5.1.3.1.1 All-Cause Hospitalizations

See [Section 5.1.3.1](#).

5.1.3.1.2 Prolonged severe (Grade 4) neutropenia (duration > 5 days)

See [Section 5.1.3.1](#).

5.1.3.2. Best Overall Response, Duration of Response, and Progression-Free Survival

For tumor assessment, all sites of disease will be assessed radiologically by CT or MRI at screening, every 6-9 weeks thereafter as determined by the protocol, until the date of (i) disease progression as defined by RECIST Version 1.1 (Eisenhauer et al, 2009); or (ii) withdrawal of consent; or (iii) receiving subsequent anti-cancer therapy, whichever is earlier. At each tumor assessment visit, the overall visit response by RECIST will be determined two ways: (1) derived programmatically using the information from target lesions (TL), non-target lesions (NTLs) and new lesions as entered into the eCRF, and (2) by the investigator and collected in the eCRF.

For all patients, the RECIST tumor response data will be used to determine each patient’s visit response according to RECIST Version 1.1 and the best overall response (BOR).

5.1.3.2.1 Target Lesions (TLs)

Measurable disease is defined as having at least one measurable lesion at baseline which is

- ≥ 10 mm in the longest diameter (LD) (except lymph nodes which must have short axis ≥ 15 mm) with computed tomography (CT) or magnetic resonance imaging (MRI); or
- ≥ 10 mm caliper measurement by clinical exam (lesions which cannot be accurately measured with calipers should be recorded as non-measurable); or
- ≥ 20 mm by chest X-ray.

Previously irradiated lesions (or lesions treated with loco-regional therapies) may be considered measurable if unequivocal growth of the lesion has been demonstrated. A patient can have a maximum of 5 measurable lesions representative of all involved organs (maximum of 2 lesions per organ, both the lymph node and skin will be considered as a single organ) recorded at

baseline and these are referred to as target lesions. If more than one baseline scan is recorded, then measurements from the one that is closest to start of treatment will be used to define the baseline sum of TLs. Table 5 gives definition of TL visit responses.

Table 5 Definition of TL Visit Responses

Visit Responses	Description
Complete Response (CR)	Disappearance of all target lesions. Any pathological lymph nodes selected as target lesions must have a reduction in short axis to <10mm.
Partial response (PR)	At least a 30% decrease in the sum of diameters of target lesions, taking as reference the baseline sum of diameters as long as criteria for PD are not met.
Progressive disease (PD)	A $\geq 20\%$ increase in the sum of diameters of target lesions and an absolute increase of $\geq 5\text{mm}$, taking as reference the smallest sum of diameters (i.e. nadir) since treatment started including the baseline sum of diameters.
Stable disease (SD)	Neither sufficient shrinkage to qualify for PR nor sufficient increase to qualify for PD.

Rounding of TL data

For calculation of PD and PR for TLs percentage changes from baseline and previous minimum should be rounded to 1 decimal place before assigning a target lesion response. For example 19.95% should be rounded to 20.0% but 19.94% should be rounded to 19.9%.

Missing TL data

If any target lesion measurements are missing then the target lesion visit response is Not Evaluable (NE). The overall visit response will also be NE, unless there is a progression of non-target lesions or new lesions, in which case the response will be PD.

TL too small to measure

If a target lesion becomes too small to measure a value of 5mm will be entered into the database and used in TL calculations, unless the radiologist has indicated and entered a smaller value that can be reliably measured.

Lesions that split

If a TL splits, then the LDs of the split lesions should be summed and reported as the LD for the lesion that split.

Lesions that merge

If target lesions merge, then the LD of the merged lesion should be recorded for one of the TL sizes and the other TL size should be recorded as 0 cm.

Change in method of assessment of target lesions

CT, MRI, chest x-ray and clinical examination are the only methods of assessment that can be used within a trial, with CT and MRI being the preferred methods and clinical examination and chest x-ray only used in special cases. If a change in method of assessment occurs between CT and MRI this will be considered acceptable and no adjustment within the programming is needed.

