
Evaluate the antitumor activity of trilaciclib or placebo administered in combination with E/P/A to patients with SCLC
	
 
• Occurrence of objective response (CR or PR per RECIST 1.1 as assessed by investigator)
 
• Duration of objective response (CR or PR per RECIST v1.1 as assessed by investigator)
 
• PFS (per RECIST 1.1 as assessed by investigator)
 

Determine the safety and tolerability of trilaciclib or placebo administered in combination with E/P/A in patients with SCLC
	
 
• Occurrence and severity of AEs by NCI CTCAE v4.03
 
• Occurrence and severity of AESIs for atezolizumab by NCI CTCAE v4.03
 
• Changes in laboratory parameters (hematology, chemistry, urinalysis), vital signs and ECG parameters
 
• Grade 3 and 4 abnormalities in laboratory parameters (hematology and chemistry)
 
• Occurrence and severity of infusion-related reactions
 
• Occurrence of trilaciclib dose delays and interruptions
 
• Occurrence of chemotherapy dose reductions
 
• Occurrence of chemotherapy dose delays and interruptions
 
• Occurrence of atezolizumab dose delays and interruptions
 
• Relative dose intensity of carboplatin and etoposide
 
• Occurrence of patients that discontinue study treatment because of AEs
 

Evaluate potential of trilaciclib to reduce chemotherapy-induced myelosuppression by assessing effects on multiple lineages and current standard of care interventions to treat myelosuppression (neutrophils, RBC, platelets, lymphocytes)
	
 
• All-cause hospitalizations
 
• Febrile neutropenia
 
• G-CSF administration
 
• Occurrence of Grade 3 and 4 hematologic lab values
 
• ANC nadir by cycle
 
• Prolonged severe neutropenia (duration >5 days)
 
• Platelet transfusions
 
• RBC transfusions
 
• ANC, hemoglobin, platelet counts, and lymphocyte counts over time
 
• Occurrence of ESA administration
 
• Occurrence of systemic antimicrobial administration
 

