#### 13.5.4. **Analysis of Supportive Secondary Efficacy Endpoints (Antitumor and Myelosuppression)**

The detailed derivation for these endpoints along with their analysis methods will be included in the SAPs.

For **Region 1 only**, OS will be considered as a supportive secondary endpoint and will be analyzed according to Section [13.5.2.1](#).

For **Region 2 only**, the composite MAHE endpoint will be considered a supportive secondary efficacy endpoint to be analyzed as described above (Section [13.5.3](#)).

All the remaining endpoints are relevant to both Regions.

Anti-tumor activity per Response Evaluation Criteria in Solid Tumors (RECIST 1.1) as assessed by the investigator will include the following:

- Objective response (CR or PR)
- Best overall response (BOR)
- Duration of objective response (DOR)
- Progression-free survival (PFS)

At each tumor assessment visit, an overall time point response by RECIST v1.1 will be determined programmatically using the information from target lesions, NTLs, and new lesions collected in the eCRF. BOR will be determined using visit responses until the last evaluable overall visit response prior to or on the date of (i) radiographic disease progression; (ii) withdrawal of consent to obtain scans; (iii) death; (iv) lost to follow-up; or (v) initiation of subsequent anticancer therapy, whichever is earlier.

Duration of Objective Response (DOR) is the time between first objective response of CR or PR and the first date that progressive disease is objectively documented or death, whichever comes first. Patients who do not experience objective CR or PR will not be included in the analysis. For patients with objective response of CR or PR but (i) withdrawal of consent to obtain scans; (ii) lost to follow up; (iii) initiation of subsequent anticancer therapy, or (iv) death, the DOR of this patient will be censored at the earliest date among these four.

PFS is defined as the time (number of months) from date of randomization until date of documented radiologic disease progression per RECIST version 1.1 or death due to any cause, whichever comes first. More specifically, PFS will be determined using all data until the last evaluable visit prior to or on the date of (i) radiographic disease progression per RECIST version 1.1; (ii) withdrawal of consent to obtain scans; or (iii) initiation of

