ORR, ORR_{UNCONFIRMED}, DOR and CBR will be calculated using the derived responses and investigator responses.

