5.1.3.2.5 Progression-free Survival

Since disease progression is assessed periodically, PD can occur any time in the time interval between the last assessment where PD was not documented and the assessment when PD is documented.

Hence, progression-free survival (PFS) is defined as the time (months) from date of randomization until date of documented disease progression or death due to any cause, whichever comes first. More specifically, PFS will be determined using all the assessment data up until the last evaluable visit prior to or on the date of (i) disease progression as defined by RECIST Version 1.1; or (ii) withdrawal of consent; or (iii) receiving subsequent anti-cancer therapy, whichever is earlier.

PFS will be calculated using derived responses and progression by RECIST Version 1.1 (whichever comes first) will be considered.

Death, regardless of cause, is always considered as a PD event. The detailed censoring rules for the analysis are summarized in [Table 9](#).

Table 9 Assignment of Progression or Censoring Based on Radiological Assessment

Situation	Date of Progression or Censoring	Outcome
No progression - treatment not started	Date of randomization	Censored
No progression	Date of last adequate radiological disease assessment	Censored
Treatment discontinuation for reasons other than disease progression	Date of last adequate radiological disease assessment with no documented progression	Censored
New anticancer treatment started prior to documented disease progression	Date of last adequate radiologic assessment no later than the initiation of new anticancer treatment	Censored

Situation	Date of Progression or Censoring	Outcome
Disease progression per RECIST Version 1.1	Date of the first reported progression	Progressed
Death without a PD	Date of death	Progressed

Note: An adequate radiologic assessment is defined as an assessment where the Investigator determined radiological response is CR, PR, SD, or PD. If PD and new anti-cancer therapy occur on the same day, will assume that the progression was documented first, e.g. outcome is progression and the date is the date of the assessment of progression.

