6.2.7.2.3 Analyses of DOR and PFS

The analysis method as described in [Section 6.2.7.1.3](#) for OS will be applied to PFS (derived) and DOR (investigator and derived), except DOR will exclude the Kaplan-Meier estimates for the survival rates at 3, 6, 9, and 12 months as well as the Cox proportional hazard model.

Spider plot by treatment group of % change in target lesion from baseline for each subject over time will be included based on derived assessments. Points will be included for best overall response (if CR or PR), new lesions, and end of treatment.

An event chart of the induction treatment period will also be included, with horizontal bars for each subject's cycle length and time on the x-axis, with points plotted for start and end of DOR.

For DOR, the analysis is based on the response evaluable analysis set; for PFS the analysis will be based on the ITT. The supportive data listings will also be provided.

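### PFS is run on program-derived responses only, and two SAP rules can delay a certain progression or turn it into a censoring

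*SAP*

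**What the plan says.** **Source of the PFS event.** Protocol Table 5-1 lists, as a supportive secondary endpoint, "PFS (per RECIST 1.1 as assessed by investigator". Protocol 13.5.4 also places PFS under investigator-assessed activity, but says that the time point response "will be determined programmatically using the information from target lesions, NTLs, and new lesions collected in the eCRF". SAP 5.1.3.2 sets two visit responses: one derived by program, and "2) by the investigator and collected in the eCRF". SAP 5.1.3.2.4 uses both for response endpoints: ORR, unconfirmed ORR, "DOR and CBR will be calculated using the derived responses and investigator responses". For PFS, SAP 5.1.3.2.5 states: "PFS will be calculated using derived responses and progression by RECIST Version 1.1 (whichever comes first) will be considered". SAP 6.2.7.2.3 then says that the OS method "will be applied to PFS (derived) and DOR (investigator and derived".

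**Missing target lesions.** SAP 5.1.3.2.1: "If any target lesion measurements are missing then the target lesion visit response is Not Evaluable (NE". The overall visit is then also NE unless non-target lesions progress or a new lesion appears. No exception covers measured lesions that already meet the progression criteria. Protocol 11.1.3.1 keeps NE for visits with too little information to assign another category.

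**Censoring.** SAP Table 9 has a row for "New anticancer treatment started prior to documented disease progression", which censors the patient at the last adequate assessment up to the start of that treatment. The note under the table calls an assessment adequate when the investigator's response is CR, PR, SD or PD.

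**The concern.** PFS is the only one of these antitumour endpoints without a planned run on the investigator's response, and the visible SAP text gives no reason. Relying on the derived response would matter little if that response always recognised progression that the data prove. The missing-lesion rule means that it does not.

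The consequence depends on what happens next. If scanning continues, the derived event moves to a later scan. If the investigator's call ends scanning or leads to new therapy, the patient may be censored because of the progression itself, which is informative censoring. At stake is the accuracy of PFS dates and the event count for the antitumour-activity objective. The primary and key secondary myelosuppression tests are not affected.

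**Working it through.** The documents give no PFS sample size, power or event count, so there is no plan figure to reproduce. The check covers the logic of the rules and the arithmetic of a lower bound.

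**1. When do the measured lesions alone prove progression?** SAP Table 5 requires a rise of at least 20% and at least 5 mm over the smallest previous sum, S. A missing diameter cannot be below 0 mm, so the true sum is at least the measured sum, M. Progression is therefore certain if (M − S)/S ≥ 20% and M − S ≥ 5 mm.

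Illustration with assumed diameters, S = 50 mm (lesion A 30, lesion B 20), B not measured at the next scan:

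| Lesion A now (= M) | Rise | Proven? | SAP rule |
|---|---|---|---|
| 62 mm | 12/50 = 24.0%, 12 mm | yes | NE |
| 60 mm | 10/50 = 20.0%, 10 mm | yes | NE |
| 59.9 mm | 9.9/50 = 19.8%, 9.9 mm | no | NE |

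In the first two rows no value of B could reverse the conclusion. The information is adequate in the protocol's sense, but the visit is NE. In the third row NE is right.

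**2. How demanding is that condition?** Suppose the missing lesion made up a share f of S, and S is at least 25 mm so that the 20% criterion governs. The measured lesions must grow from (1 − f)S to at least 1.2S, a growth of 1.2/(1 − f) − 1.

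- f = 0.2: 1.2/0.8 − 1 = 50%
- f = 0.4: 1.2/0.6 − 1 = 100%
- f = 0.5: 1.2/0.5 − 1 = 140%

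In the 62 mm example, f = 20/50 = 0.4 and lesion A grew by 32/30 = 107%. The rule therefore matters only with large growth in the measured lesions, no new lesion and no non-target progression.

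**3. What happens to such a visit?** If scans continue, the derived event comes about 6 or 9 weeks later on study drug. But scheduled scans run only until progression (Protocol 6.1.4), and scans after study drug are for patients who had not progressed when it stopped (Protocol 10.7). There may be no later scan. Then the patient is censored, or a later death becomes the event.

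**4. Table 9 applied to a scan the investigator calls PD and the program calls NE, followed by new therapy.**

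- Event source (derived): no progression.
- Adequacy source (investigator): PD, so the scan is adequate.
- Result: censored as progression-free on that scan.

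With the investigator as the only source, the scan would be an event. With the derived response as the only source, an NE scan would not be adequate and censoring would fall on an earlier scan. Only the mixture places the censoring on the scan called progression.

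**5. Scale.** SAP 6.2.13 sets final PFS at 80% of patients progressed: 0.80 × 100 = 80, or 0.80 × 106 = 84.8, about 85. Let q be the share of progressions meeting every condition in steps 1 and 2. The documents do not give q. Assumed values of 0%, 2%, 5% and 10% give 0, 1.6, 4.0 and 8.0 of 80 events, or 0, 1.7, 4.25 and 8.5 of 85. Step 2 points to the low end.

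**The case against.** The strongest reply is that derived PFS is what the protocol intends. Protocol 13.5.4 prescribes programmatic time point response within its investigator-assessed section. The inputs are also the site's own: non-target response rests on the investigator's assessment and new lesions come from the eCRF (SAP 5.1.3.2.2), so the program adds mainly target-lesion arithmetic. The SAP supersedes the protocol (Protocol 13), and its list of changes from the protocol (SAP 7) is redacted, so a declared change cannot be excluded. This stands as far as it goes. A reader might infer that the protocol's endpoint is simply not analysed, but the documents show a tension between Table 5-1 and 13.5.4. A reader might also take Protocol 11.1.4 to fix the PFS source. That sentence applies only to analyses that include the investigator's progression date, for patients treated beyond progression; it does not choose the source. None of this cures the two rules, which are faults within derived PFS.

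Second, the NE rule agrees with Protocol Table 11-1 and SAP Table 7, which give NE for a target response that is not evaluable or not fully evaluated, with no other sign of progression. That is so. But Protocol 11.1.3.1 says when NE may be used, and proven progression falls outside it.

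Third, the SAP 5.1.3.2.5 sentence on PFS is garbled, and Table 9 dates the event at the first reported progression, so investigator-called progression might be meant to count. The label in SAP 6.2.7.2.3 and the omission of PFS from the both-sources list favour derived only. The ambiguity itself needs correcting.

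Fourth, exposure is limited. New lesions, non-target progression and death count as events, treatment beyond progression may leave only a delay, and the trial is double-blind. All of this stands.

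**Conclusion.** The point holds as a consistency and event-dating problem of low to moderate severity. PFS is planned on derived responses only; a visit with certain target progression can be NE; and Table 9 can censor a patient on the scan the investigator called progression. These follow from the text without assumptions about the data.

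The size does not. The counts in the working rest on an assumed q, and the conditions are demanding, so few events are likely to be affected. A reader might infer a bias in favour of one arm or a material change in the hazard ratio; nothing in the documents supports either. Nor do they make PFS the test that trilaciclib does no harm: SAP 5.1.2.4 gives that role to OS. PFS is a supportive secondary endpoint outside the multiplicity procedure.

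**What to change.** - In SAP 5.1.3.2.1, add that when a target lesion is missing but the measured lesions alone meet both progression thresholds against the smallest previous sum, the target response is PD. Adjust the matching row of SAP Table 7.
- In SAP 5.1.3.2.5 and 6.2.7.2.3, add PFS by investigator response alongside derived PFS, as for DOR, and state which is the main analysis. Rewrite the unclear sentence on the PFS source.
- In SAP Table 9, use one response source within each analysis for both events and adequate assessments.
- Reconcile Protocol Table 5-1 with Protocol 13.5.4, or state in the SAP how the two are read together.

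The cost is SAP wording, a small change to the derivation program and one further PFS run. The investigator's response is already collected in the eCRF, so no new data are needed. The changes should be settled before unblinding.

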5.1.3.2.2 Non-Target Lesions (NTLs) and New Lesions

The non-target lesion response will be based on the Investigator’s assessment of NTLs as [Table 6](#):

Table 6 Definition of NTLs Visit Responses

Visit Responses	Description
CR	Disappearance of all NTLs present at baseline with all lymph nodes non-pathological in size (<10mm short axis).
PD	Unequivocal progression of existing NTLs, which may be due to an important progression in one lesion only or in several lesions
Non-CR/Non-PD	Persistence of one or more NTLs with no evidence of progression
NE	Only relevant when one or some of the NTLs have not been assessed and in the Investigator’s opinion they are not able to provide an evaluable overall NTL assessment.

New lesions

New lesions (target or non-target) will be identified via a separate eCRF page. The absence and presence of new lesions at each visit should be listed alongside the TL and NTL visit responses.

A new lesion indicates progression, so the overall visit response will be PD irrespective of the TL and NTL responses.

5.1.3.2.3 Time Point Response (TPR)

[Table 7](#) defines how the previously defined TL and NTL visit responses will be combined with new lesion information to give a TPR. The possible TPRs at a visit are CR, PR, SD, Non-CR/Non-PD, PD, and NE.

Table 7 Evaluation of Time Point Response: Patients with Baseline Target Lesions

Target Lesions	Non-target Lesions	New Lesions	Overall Response
CR	CR	No	CR
CR	Non-CR/Non-PD	No	PR
CR	Not evaluated	No	PR
PR	Non-PD/not all evaluated	No	PR
SD	Non-PD/not all evaluated	No	SD
Not all evaluated	Non-PD	No	NE
PD	Any	Yes or No	PD
Any	PD	Yes or No	PD
Any	Any	Yes	PD

CR = complete response, PR= partial response, SD = stable disease, PD = progressive disease, NE = not evaluable

At each visit, patients will be programmatically assigned a RECIST Version 1.1 TPR of CR, PR, SD, PD or NE depending on the status of their disease compared to baseline and previous assessments as discussed in the [Sections 5.1.3.2.1 and 5.1.3.2.2](#).

For a scheduled tumor scan assessment, it is expected that there will be a variation for the actual timing of scans among target, non-target, and new lesions. In assigning a date for the derived overall assessment at a visit, the earliest date collected at that visit will be used. Within a

grouped timepoint, if there are multiple assessments on different dates for the *same* target lesions, the last assessment will be used.

5.1.3.2.4 Best Overall Response (BOR) and Duration of Response (DOR)

BOR will be determined using TPRs up until the last evaluable TPR prior to or on the date of (i) disease progression as defined by RECIST Version 1.1; or (ii) withdrawal of consent; or (iii) receiving subsequent anti-cancer therapy, whichever is earlier.

A patient's BOR will be determined based on [Table 8](#). For data-driven scenarios which may not be covered by [Table 8](#), the BOR will be reviewed and determined by the medical advisors and statisticians prior to locking the database.

For patients who are treated beyond progression and subsequently have a response, the best overall response is only derived from assessments up to and including the time of the initial progression (i.e., it will not include the response after the patient has progressed).

There are two ways of assigning BOR for a patient when the minimum interval for confirmation of CR and PR is not satisfied or if there are no confirmatory scans for CR and PR:

- Adding two more response categories as: unconfirmed CR, unconfirmed PR;
- Assigning BOR as SD, that is, both the unconfirmed CR and unconfirmed PR will be SD.

Both ways of assigning BOR will be implemented.

The number and percentage of patients in each category of derived BOR (Confirmed CR, Confirmed PR, SD, PD, or NE) will be summarized.

Table 8 Best Overall Response When Confirmation of CR and PR are Required [a]

First TPR	Second TPR	Best overall response*^ for ORR	Best Overall Response for ORR _{UNCONFIRMED}
CR	CR	CR	CR
CR	PR	SD [b] or PD	Unconfirmed CR
CR	SD	SD [b] or PD	Unconfirmed CR
CR	PD	SD [b] or PD	Unconfirmed CR
CR	NE or NA	SD [c] or NE or NA	Unconfirmed CR
PR	CR	PR	Unconfirmed CR
PR	PR	PR	PR
PR	SD	SD [d]	Unconfirmed PR
PR	PD	SD [b] or PD	Unconfirmed PR
PR	NE or NA	SD [c] or NE or NA	Unconfirmed PR
NE	NE	NE	NE
NE	CR	SD	Unconfirmed CR
NE	PR	SD	Unconfirmed PR
NE	SD	SD	SD
NE or NA	PD	PD	PD
SD	PD	SD [b] or PD	SD [b] or PD
SD	CR	SD	SD
SD	PR	SD	SD
SD	SD	SD	SD
SD	NE or NA	SD [c] or NE or NA	SD [c] or NE
PD	No further evaluation	PD	PD

CR = complete response, PR= partial response, SD = stable disease, PD = progressive disease, NE = not evaluable, NA = not available, ORR = Objective Response Rate

- a. The minimum interval for confirmation of CR and PR is 4 weeks.
- b. Best response will be SD if the first time point overall response is after 35 days on study. Otherwise, the best response will be PD.
- c. Best response will be SD if the first time point overall response if after 35 days on study. Otherwise, the best response will be NE.
- d. Best response will be SD provided the criteria for PD have not been met from the first to second assessment.

* A best overall response of SD can only be made after the subject is on study for a minimum of 35 days (counted from Cycle 1 Day 1). If the subject is on study for less than 35 days, any tumor assessment indicating stable disease before this time period will have a best response of NE unless PD is identified.

^Subsequent documentation of a CR may provide confirmation of a previously identified CR even with an intervening NE (e.g., CR NE CR). Subsequent documentation of a PR may provide confirmation of a previously identified PR even with an intervening NE or SD (e.g., PR NE PR or PR SD PR). However, only one (1) intervening NE or SD will be allowed between PRs for confirmation. Note: in the following scenario, PR SD NE PR, the second PR is not a confirmation of the first PR.

Objective response rate (ORR) will be calculated using two methods:

Method #1: ORR will be calculated using a strict interpretation of RECIST Version 1.1.

Objective response will be derived as no/yes (0/1) variable. Patients with a BOR of confirmed CR or PR will be assigned ‘Yes’. Patients not having a BOR of confirmed CR or PR will be assigned ‘No’. Hence, ORR is defined as the proportion of patients with objective response being “Yes”.

Method #2: ORR_{UNCONFIRMED} will be calculated using all responses regardless of confirmation. Objective response will be derived as no/yes (0/1) variable. Patients with a BOR of confirmed CR, confirmed PR, unconfirmed CR or unconfirmed PR will be assigned “Yes”. All patients with other BOR values will be assigned “No”. Hence, ORR_{UNCONFIRMED} is defined as the proportion of patients with objective response being “Yes”.

Duration of Response (DOR) is the time between first response by RECIST Version 1.1 of CR or PR and the first date that progressive disease is documented by RECIST Version 1.1, or death. Patients who do not experience PD or death will be censored at the last tumor assessment date. Only those patients with confirmed responses will be included in this analysis. Censoring will follow the rules outlined below for PFS in [Section 5.1.3.2.5](#).

Clinical benefit rate (CBR) is defined as the proportion of patients with a BOR of confirmed CR, confirmed PR, or SD.

ORR, ORR_{UNCONFIRMED}, DOR and CBR will be calculated using the derived responses and investigator responses.

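### SAP Table 8 scores stable disease followed by CR or PR as SD in the unconfirmed-response column, which contradicts the definition of that rate (minor)

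*SAP*

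**What the plan says.** SAP 5.1.3.2.4 gives two ways to handle a CR or PR that lacks a qualifying confirmatory scan, and both are to be implemented. One is "Adding two more response categories as: unconfirmed CR, unconfirmed PR"; the other assigns SD. The text makes no exception for a response that follows stable disease.

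Method #2 in the same section defines ORR_UNCONFIRMED, which "will be calculated using all responses regardless of confirmation". The rule is binary: "Patients with a BOR of confirmed CR, confirmed PR, unconfirmed CR or unconfirmed PR will be assigned “Yes", and "All patients with other BOR values will be assigned “No". A best overall response of SD is therefore a non-response.

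Table 8 supplies the best overall response: "A patient's BOR will be determined based on" that table. It takes a first and a second time point response and has one column for the confirmed rate and one for the unconfirmed rate. The rows with a non-evaluable first scan read "NE CR SD Unconfirmed CR" and "NE PR SD Unconfirmed PR" (first response, second response, confirmed column, unconfirmed column). The rows SD-then-CR and SD-then-PR carry SD in both columns.

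Review by medical advisors and statisticians before database lock is provided "For data-driven scenarios which may not be covered by" Table 8.

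**The concern.** The unconfirmed rate exists to capture responses that have not been, or could not be, confirmed. A patient with SD at the first scan and a PR at the second has such a response, yet the table makes that patient a non-responder. Had the first scan been non-evaluable, the same PR would count.

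The response criteria do not justify the distinction. SAP Table 5 measures PR against the baseline sum of diameters, so an intervening SD does not weaken a later PR.

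Patients with only two scans are foreseeable. Scans come about every 6 weeks early in the study, and SAP 6.2.13 includes an ORR analysis in a data cut made once all patients have had the opportunity for at least 12 weeks of treatment. If the table and the definition disagree at that point, someone must choose between them, and that choice should not be left until after unblinding.

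**Working it through.** The plan states no value for either response rate, so there is no figure to reproduce. The check is of the classification rule, followed by a simple scale calculation.

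**Step 1: count the rows of Table 8.** There are 21 rows, of which 14 have a CR or PR at the first or second time point.

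| Rows containing a CR or PR | Number | Unconfirmed column |
|---|---|---|
| CR first (then CR, PR, SD, PD, NE or NA) | 5 | CR or Unconfirmed CR |
| PR first (then CR, PR, SD, PD, NE or NA) | 5 | PR, Unconfirmed PR or Unconfirmed CR |
| NE, then CR or PR | 2 | Unconfirmed CR, Unconfirmed PR |
| SD, then CR or PR | 2 | SD, SD |

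So 5 + 5 + 2 = 12 of 14 rows are scored as a response under Method #2. The other two are SD-then-CR and SD-then-PR. A PR followed by progression counts; a PR preceded by stable disease does not.

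**Step 2: look for an explanation.** Footnotes a to d and the two marked notes cover the 4-week confirmation interval, the 35-day minimum for SD, and confirmation across intervening NE or SD scans. None says that an earlier SD cancels a later unconfirmed response. The review clause does not reach these rows, because the table covers them.

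**Step 3: direction.** The two cells can only turn a response into a non-response. Any effect on ORR_UNCONFIRMED is therefore downward, in whichever arm it occurs.

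**Step 4: scale.** Change in an arm's rate = k / n, with k patients affected among n. The documents give approximately 100 patients (n = 50 per arm) and an adjusted sample size of 106 (106 / 2 = 53 per arm). The documents do not give k, so the values below are assumptions.

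| k (assumed) | n = 50 | n = 53 |
|---|---|---|
| 1 | 2.0 points | 1.9 points |
| 2 | 4.0 points | 3.8 points |
| 3 | 6.0 points | 5.7 points |
| 5 | 10.0 points | 9.4 points |

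These are planned randomised numbers. SAP 6.2.7.2.2 bases response analyses on the response evaluable set, whose size is not stated. A smaller n makes each patient count slightly more.

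**Step 5: sequences of scans under two possible readings of Table 8, as written.**

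| Sequence | First two scans only | Every successive pair, with a missing next scan taken as NA |
|---|---|---|
| SD, PR, no further scan | SD | Unconfirmed PR (via the PR-then-NE-or-NA row) |
| SD, PR, PD | SD | Unconfirmed PR (via the PR-then-PD row) |
| SD, SD, PR, no further scan | SD | Unconfirmed PR (via the PR-then-NE-or-NA row) |

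The size of the understatement therefore depends on a reading that the SAP does not specify. If only the two cells were changed, the first two sequences would be counted under either reading. SD, SD, PR would still be scored SD under the first reading.

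**The case against.** The strongest reply is that Table 8 is meant to be applied to successive pairs of scans. It has rows for a CR or PR followed by NE or NA, so a patient with SD, then PR, then nothing has a PR-then-NA pair and is scored Unconfirmed PR. A note under the table discusses sequences of three and four scans, so the table is evidently not confined to the first two. On this reading the affected patients are recovered, and the surrounding text makes the intent clear in any case.

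Part of this stands. It is a possible reading, and a reader who inferred that no reading rescues a two-scan patient would be going too far. But the SAP does not state the rule. Nor does the rule explain why NE-then-PR is scored Unconfirmed PR directly, when the same PR-then-NA pair would have been available there, while SD-then-PR is scored SD. The table as written still conflicts with the definition.

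Two further replies stand in full. The affected group may be small: both documents call for a confirmatory scan at least 4 weeks after a first response, so an unconfirmed response at the last available scan needs drop-out, a data cut or a similar event. And little rests on the rate. SAP 6.2.7.2.2 summarises it by number and percentage, names only ORR and CBR for exact intervals and only ORR for the stratified comparison, and the rate lies outside the multiplicity procedure.

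**Conclusion.** The inconsistency is real and minor. Two cells of Table 8 contradict the definition of the rate they feed and are out of line with the other 12 rows that contain a response. Under a literal reading, ORR_UNCONFIRMED can only be understated, by about 2 points per affected patient at roughly 50 per arm. Under a successive-pair reading, some or all of those patients are recovered.

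A reader might infer that the unconfirmed rate will be too low by some particular amount, such as 5 to 10 points. The documents do not support this. Such a figure only restates an assumed share of patients whose sole CR or PR follows SD and goes unconfirmed, and neither document gives that share or the response evaluable denominator.

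A reader might also infer a biased treatment comparison. The rule is the same in both arms, and the documents offer no evidence that the timing of first response differs between them. A shift in the contrast is possible but not shown.

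The fault does not reach confirmed ORR, where SD is the proper entry for these two rows. It does not reach DOR (confirmed responders only), CBR (SD already counts), PFS or the primary endpoints.

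**What to change.** In the ORR_UNCONFIRMED column of SAP Table 8, change SD-then-CR to Unconfirmed CR and SD-then-PR to Unconfirmed PR. Leave the confirmed column as it is.

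Add one sentence: for more than two time points, the unconfirmed best overall response is the best CR or PR at any evaluable time point up to the existing cut-off for best overall response (progression, withdrawal of consent or subsequent anticancer therapy, whichever is earliest). Without it, a sequence such as SD, SD, PR stays unresolved.

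The cost is two table cells, one sentence and the matching derivation code. No data collection, sample size or test changes. Make the change before database lock and unblinding, so that the choice between table and text is not made with results in view.
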